2.1.1 Primary Objectives

- 1. To improve the understanding of the care needs and holistic developmental journeys of all CYP attending NHS Gender Services.
- 2. To understand how the developmental trajectories and short to medium-term outcomes of CYP with gender incongruence are influenced by differences amongst CYP and their life experiences.

2.1.2 Secondary Objectives

- 1. To improve understanding of how care options are experienced by CYP and their parents/carers/legal guardians.
- 2. To develop a novel interview-based outcome measure that focuses on CYP's aspirations and goals from gender care.
- 3. To explore similarities and differences in the holistic perspectives of CYP and their parents/carers/legal guardians to gain a comprehensive understanding of how gender incongruence affects CYP.

3. Participants & Recruitment.

3.1 Participants

Participants will include CYP of any age referred to the CYPGS, along with their parent(s), caregiver(s), or legal guardian(s) following acceptance of the referral. CYP may be seen in the service up to age 18 years, at which point they are referred to adult Gender Services. Referrals to the CYPGS may be made by an NHS-commissioned secondary care level paediatric service or CYP mental health service. For a referral to be accepted, it must indicate that the CYP is experiencing concerns or distress related to their gender identity. The absence of a lower age limit applies only to the HORIZON study and not to other studies in PATHWAYS which have a greater focus on GnRHa. The purpose of the HORIZON study is to provide a comprehensive description of the presenting characteristics and developmental trajectories of all CYP presenting to the service, in order to improve care for the entire population.

Only CYP and their parents/carers/legal guardians who attend a first assessment appointment in the CYPGS will be included. CYP remain eligible to participate in the study even after discharge from the services, including those who transition to adult services. All CYP and their parents/carers/legal guardians will be followed up annually, even if they no longer remain within the service and/or have been discharged, unless they withdraw from the study.

CYP and their parents/carers/legal guardians who attended a first appointment in the new CYPGS and were discharged prior to the study onset will also be contacted to provide them with the opportunity to participate.

3.2 Eligibility criteria

3.2.1 INCLUSION CRITERIA

- 1. The CYP has an accepted referral to CYPGS, or has already attended an appointment at a CYPGS.
- 2. The CYP is awaiting or has received their first appointment with the service at the time of completing baseline measures.
- 3. Valid assent/consent has been obtained:
 - a) For CYP under the age of 16 at recruitment providing self-reports:
 - i. Parent/legal guardian gives consent for them to participate AND
 - ii. CYP gives assent to participate.CYP is deemed to have capacity to consent by their clinician and gives consent to participate.
 - b) For CYP 16 years and above providing self-report information:
 - i. CYP gives consent to participate. OR
 - ii. Personal Consultee gives consent for the CYP to participate if the CYP lacks capacity to consent.
 - c) For parent-reported measures for CYP under the age of 16 at recruitment: Parent/legal guardian consents to their own participation to provide parent-reported measures.
 - d) For parent-reported measures for CYP 16 years and over at recruitment: Parent/legal guardian consents to their own participation to provide parent-reported measures and CYP consents to parent/legal guardian completing measures.

3.2.2 EXCLUSION CRITERIA

- 1. CYP did not attend a first appointment at CYPGS.
- 2. CYP deemed unsuitable in the opinion of the investigator for clinical or other reasons.

3.3 Informed consent

All CYP and their parents/carers/legal guardians attending the CYPGS will receive the participant information sheet (PIS) about the study and will be invited to provide assent/consent electronically via the Medrio eConsent module (see section 5.1.2).

Assent/consent from CYP and parents/legal guardians will be considered semi-independent. That is, a parent may choose to provide information about their CYP, even if that CYP declines to participate by providing self-reports. For CYP under age 16 years, parental consent for them to participate is generally required, but can be given even if the parent decides not to participate themselves. CYP 16 years and over will be asked whether they consent to their parent or another trusted adult completing informant versions of questionnaires.

For CYP who turn 16 years during the study period, consent will be taken prior to or at the next assessment point. Informed assent/consent will be obtained from CYP and parents/legal guardians at baseline before any assessment measures are completed. Assent/consent will be documented electronically, and participants will be assured that their decision to participate (or not) will not affect their access to care or future care pathways. This includes endocrine care and involvement in the randomised controlled trial evaluating gonadotropin releasing hormone analogues (GnRHa), PATHWAYS TRIAL.

Parents/legal guardians of CYP <16 and YP 16 years and older will be contacted by the CYPGS to obtain consent and provide their email addresses for PATHWAYS HORIZON researchers to contact them about the study. The PIS will then be sent to participants with other information about their first appointment. Given the relatively low risk nature of this questionnaire study, after receiving the PIS, participants will have the following options:

- 1. To assent/consent electronically.
- 2. To request that a researcher gets in touch to tell them more about the study.
- 3. To delay the decision until after their first appointment in the CYPGS (and be contacted then to answer any questions).
- 4. To decline participation.

The process of contacting and obtaining assent/consent is as follows:

- 1. The health care team will send the CYP and parent/legal guardian an email explaining that the CYPGS is collaborating with PATHWAYS and asking for their consent for the research team to get in touch to tell them about the study ("consent for contact"). This will ordinarily be sent with information about the first appointment but will be sent separately for those who have already attended a first appointment.
- 2. For those participants who agree to be contacted, the health care team (clinic) will notify the research team who will send the PIS and assent/consent, with their details. They may speak to a researcher in person at the CYPGS, by telephone or MS Teams video call to answer any questions.
- 3. The health care team at the CYPGS will maintain a screening log of participants contacted and their response. For those not providing consent for contact, their file will be flagged at the first appointment. A member of the health care team will then check whether they have considered the consent for contact and chosen not to consent, whether this had not been considered, or they had neglected to respond (as is the experience in other services operating a consent for research contact policy). An anonymised copy of the screening log containing CYP age at referral, length of time on the waiting list, birth-registered sex, ethnicity, index of multiple deprivation decile, known neurodevelopmental diagnosis and whether a member of the health care team requested the CYP was not contacted/included in the study will be shared with the PATHWAYS HORIZON research team in order to understand selective research uptake.
- 4. There will be a small number of participants who have previously attended and been discharged from the CYPGS. They will receive the same email regarding consent for contact. If they do not respond, they will receive one phone call from the clinic to check whether they have received and read the letter and to record their preferences. For those consenting to contact, the same procedure will be followed.
- 5. When the CYP <16 years provides assent but parental consent is lacking, a member of the health care team in the CYPGS will get in touch to remind them that parental consent is required. CYP and parents/carers/legal guardians who have not responded may be contacted by a researcher or clinic administrator to ensure they have received the materials.
- 6. Informed consent from one parent/legal guardian for CYP under 16 years and consent from CYP 16 years and older will be obtained prior to completion of baseline measures. This consent will be taken separately for CYP self-report and parental report. There is no upper time limit for CYP and their parents/carers/legal guardians to consider participation and they will be encouraged to ask any further questions about the study, including referring to the study website which will develop a section specifically for study participants.
- 7. It is possible there will be rare instances in which the CYP wishes to participate but the parent/legal guardian does not provide informed consent. In such instances, consideration of the CYP's ability to provide informed consent will be delayed until they have been assessed in the CYPGS. The clinical keyworker or their clinical delegate will be requested to assess the CYP's ability to provide informed consent and to consider any disadvantages for their clinical care if they participate against parent support (e.g., family disharmony). The clinician's opinion regarding the CYP's ability to provide informed consent will be recorded in the clinical notes. If they deem the CYP able to provide consent, they will provide an additional signature on the

consent form. Professionals conducting an assessment will have access to training and consultation from a Consultant Paediatrician or Psychiatrist based in the CYPGS.

Study participation will routinely be recorded in the participant's medical record unless a risk is identified. In such cases, the local risk protocol will be followed, which may lead to CYPGS triggering safeguarding or other referrals as necessary at the local site.

Families with CYP unable to complete the baseline assessments, e.g., due to significant intellectual disability, will still be invited to participate in completing parent-reported and clinician-recorded measures. Families with parents/carers/legal guardians who are unable to complete study questionnaires will still be allowed to participate in the study provided they can provide informed written consent, for the CYP (if less than 16 years) to take part in the study.

The mental capacity assessment as per the Mental Capacity Act involves a two-stage assessment: 1) whether the participant has an impairment of or disturbance to, the functioning of the brain; 2) whether the impairment impacts the participant's ability to make a particular decision (e.g. consent to the research study). A participant will be considered unable to make a particular decision if they are unable to understand the information relevant to the decision; retain the information; use or weigh the information; communicate their decision (by any means). For participants that are unable to consent, the parent or the legal guardian will be invited to be the participant's consultee on their wishes and feelings and whether or not they should take part. Where possible, a second parent will be the consultee, who is not the nominated parental informant for questionnaires, to reduce any possible conflict of interest. The personal consultee will get a Consultee Information Sheet informing them about the study and will complete the Consultee Declaration Form. We will provide the Participant Information Sheet +16 and Easy Read Participant Information Sheet +16, as appropriate.

Only participants who provide informed consent to be contacted regarding future research when consenting to participation in PATHWAYS Horizon will be contacted for the novel outcome measure study. Those contacted will receive the novel outcome measure PIS and will be invited to provide assent/ consent to the following:

- 1. To participate in the novel outcome measure study through completing an interview and research measures.
- 2. For information already being collected from routine clinical outcomes and clinical records as part of service evaluation to be included in research data.
- 3. For long-term follow-up of data linkage to health and education records.
- 4. To be contacted to arrange an interview.
- 5. For the interview to be audio recorded for the purposes of data collection.
- 6. For the CYP's General Practitioner to be informed of their participation in the research.

For a visual representation of the possible consent/assent scenarios in PATHWAYS HORIZON, please refer to the flowchart in Annex 1.

3.4 Assessments and assessment windows

Initial data collection for new cases will be at baseline, defined as just before the first appointment, on the day of the first appointment, or within five months of the first appointment. Subsequent data collection will take place annually, with timing related to the initial assessment in the CYPGS. CYP and parents/carers/legal guardians who decline/defer participation at initial contact may join PATHWAYS HORIZON at a later date, which will include baseline characterisation.

3.4.1 Assessment windows

Timing of annual assessments will be based on the date of the first assessment in the CYPGS. For all participants, the subsequent annual data collection windows will commence at 6 weeks prior to their annual date and will extend until 5 months after their annual date.

All participants will be contacted via text or email as preferred, 6 weeks prior to their annual date. Participants who do not respond will be contacted again on their annual date. A further reminder will be sent 2 weeks after their annual date for any participants who have not responded, at which point they will also be asked whether they can be contacted directly. If no response has been received after 3 reminders, a member of the research team will follow-up with the participant via phone to offer their assistance. At each point of contact participants will be given the option to withdraw from the study should they no longer wish to participate.

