8.4.1 STATISTICAL METHODS FOR PRIMARY OUTCOME

The primary outcome will be analysed using a linear mixed model. This will account for the repeated measured design, and using maximum likelihood estimation allows for handling of missing follow-up data.

The fixed effects in the model will be timepoint, gender incongruence, age, site, neurodevelopmental conditions. The random effects in the model will be participant, to allow for random intercepts.

Estimates presented from this model will be point estimates and the 95% confidence intervals of those estimates.

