8.8 METHODS TO HANDLE MISSING DATA

Missing data will be dealt with using the analysis method chosen. Using a linear mixed model with maximum likelihood estimation deals with missing data under the Missing at Random method. To determine if the data is not Missing at Random, we will conduct a sensitivity analysis for Missing Not at Random (MNAR).

Multiple imputation will be considered as a method to deal with missing data in relation to the level of missingness in the outcome. Participants will only have outcomes imputed for timepoints that they could have attended, in relation to the year they were consented into the study. For example, a participant consented with only 3 years of follow-up possible will not have a 4- or 5-year follow-up outcome imputed.

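### Annual waves run from the first clinic appointment while baseline can fall months later, and the random-intercept model can understate standard errors for trajectory effects over longer follow-up

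*Protocol*

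**What the plan says.** **Annual clock.** Section 3.4.1 states: "Timing of annual assessments will be based on the date of the first assessment in the CYPGS". Section 3.4 agrees: "Subsequent data collection will take place annually, with timing related to the initial assessment in the CYPGS". For all participants, each annual window "will commence at 6 weeks prior to their annual date and will extend until 5 months after their annual date".

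**Baseline.** For new cases, 3.4 has baseline "defined as just before the first appointment, on the day of the first appointment, or within five months of the first appointment". People who decline or defer at first "may join PATHWAYS HORIZON at a later date, which will include baseline characterisation". Section 3.3 adds: "There is no upper time limit for CYP and their parents/carers/legal guardians to consider participation". Waiting until after the first appointment is one of the options offered in 3.3, and 3.1 also invites families who were seen and discharged before the study began.

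**Model.** Section 8.4.1 lists timepoint among the fixed effects and continues: "The random effects in the model will be participant, to allow for random intercepts". Sections 8.4.2.1 and 8.4.2.2 carry the same effects to the continuous and binary secondary outcomes. Section 8.6 plans subgroup analyses through interaction terms and stratified models. Primary objective 2 (2.1.2 precedes only the secondary ones; the objective is in 2.1.1) asks how trajectories depend on differences between young people.

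**Imputation.** Section 8.8 limits imputation to waves the participant could have attended, judged "in relation to the year they were consented into the study".

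**The concern.** Three clocks are in play: the clinic appointment sets the annual dates, the date of joining sets the baseline, and the year of consent sets which waves count as possible. For someone who joins promptly they nearly coincide. For someone who joins late they do not, and the protocol does not say which annual wave such a person takes next or how soon after the entry assessment. A change from baseline to Month 12 can then cover very different lengths of time.

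Separately, a random intercept alone allows no individual variation in rate of change beyond what the fixed effects explain. Where such variation exists, tests of whether a characteristic alters the trajectory, which is the question in primary objective 2, reject too often and their confidence intervals are too narrow.

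**Working it through.** The protocol gives no figure for the baseline-to-wave gap or for the error rate of a trajectory test, so there is no stated figure to reproduce.

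**1. Gap from baseline to Month 12** (inputs: 3.4 and 3.4.1; 6 weeks = 42/365.25 × 12 = 1.38 months)

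- Month 12 window: 12 − 1.38 = 10.62 to 12 + 5 = 17 months after first appointment.
- Shortest gap with an in-window baseline: 10.62 − 5 = 5.62 months.
- Longest: 17 − 0 = 17 months, slightly more if baseline is taken before the appointment (3.4 sets no lower limit).
- Joiner at month 9: 10.62 − 9 = 1.62 to 17 − 9 = 8 months.
- Joiner at month 12: the window is already open, so 0 to 5 months.
- Joiner at month 20: the Month 12 window has closed. Month 24 opens at 24 − 1.38 = 22.62, so the next gap is 2.62 to 29 − 20 = 9 months.

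If timing is uniform within windows (an assumption) and nobody joins late, the mean gap is (10.62 + 17)/2 − 2.5 = 11.3 months. If 20% join uniformly between months 5 and 10.6 (also an assumption, since the protocol gives no share), mean baseline time is 0.8 × 2.5 + 0.2 × 7.8 = 3.56 and the mean gap is 13.81 − 3.56 = 10.25 months.

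**2. Meaning of timepoint.** Section 8.4.1 does not define it. Elsewhere the word denotes a wave: 8.8 refers to attendable timepoints and gives yearly follow-ups as the example, 4.1.3 and 4.4.3 use it for annual visits, and 5.1.3 for scheduled ones.

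**3. Two clocks, worked example** (study length 5.5 years = 66 months, Section 2). Take a first appointment at study month 12 and consent at study month 30. Annual dates fall at study months 24, 36, 48 and 60, labelled Months 12, 24, 36 and 48. The Month 12 window closed at 12 + 17 = 29, before entry, so the attendable waves are Months 24, 36 and 48. From consent, 66 − 30 = 36 months remain, that is, three years. If the 8.8 rule is applied to the schedule's wave labels, Month 12 (which could not have been attended) would be imputed and Month 48 (which could) would not.

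**4. Standard errors under a random intercept only.** Assumptions: annual visits, everyone with the same number of visits T (baseline included), residual variance s² = 0.36, individual slope SD τ of 0.10 to 0.20 baseline SD per year. The protocol gives neither s² nor τ. Sxx is the sum of squared visit times about their mean.

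- True variance of a person's slope: τ² + s²/Sxx.
- Variance the random-intercept model reports: [s² + τ²·Sxx/(T − 1)]/Sxx.
- SE ratio r = √(reported/true). Type I error = 2·[1 − Φ(1.96 r)].

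Example, T = 5, τ = 0.20: Sxx = 10, true = 0.04 + 0.036 = 0.076, reported = (0.36 + 0.10)/10 = 0.046, r = 0.778, type I error 12.7%.

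| Visits T | Sxx | r at τ = 0.10 / 0.20 | Type I error | SE ratio, baseline-to-Month-12 contrast |
|---|---|---|---|---|
| 3 | 2 | 0.987 / 0.953 | 5.3% / 6.2% | 1.007 / 1.026 |
| 4 | 5 | 0.958 / 0.873 | 6.0% / 8.7% | 1.016 / 1.060 |
| 5 | 10 | 0.915 / 0.778 | 7.3% / 12.7% | 1.027 / 1.100 |

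The last column is √{2[s² + τ²·Sxx/(T − 1)]/(τ² + 2s²)}. It exceeds 1, so that one-year contrast is reported with an SE that is too large. With τ = 0, r = 1 and the model is correct.

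If correlation instead decays as AR(1) with ρ of 0.6 to 0.8, the slope SE ratio is 0.84 to 0.87 with three visits and 0.74 to 0.78 with four.

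**5. How many visits.** Recruitment covers the first 3.5 of 5.5 years, leaving 2 to 5.5 years after consent. Three visits are therefore within reach of all entrants, but five need four annual follow-ups and so entry in about the first 1.5 years.

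**The case against.** The strongest reply is that the coding of time is normally left to the SAP. Section 8.4.1 does not say that timepoint is a wave label, 8.4 refers further analysis detail to the SAP, and the first-appointment date is recorded (4.3.2), so elapsed time could be used without contradicting the protocol. This stands in part. A reader might infer that the model treats every gap as twelve months; the protocol's usage points that way but does not state it. The random-intercept structure, the late-entry rule and the consent-based count are stated, however, and are not deferred.

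A reader might also infer that gaps run from 0 to 17 months across the cohort. They do not: an in-window baseline gives at least 5.6 months, and values near zero need a late joiner and a decision to collect both assessments together. The number of late joiners is not given, and 3.3 expects few from the discharged group.

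Nor do the documents support saying that trajectory errors are too small without condition. That needs varying slopes or decaying correlation, is slight with three visits, and reverses for the baseline-to-Month-12 contrast. The interaction terms and stratified analyses in 8.6 also let groups follow different trajectories, so the model does not force everyone to change at one rate; it leaves out only the remaining individual variation. Finally, anchoring on first appointment does put every Month 12 record 10.6 to 17 months after service entry, so for that wave it is chiefly the entry assessment whose timing is loose.

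**Conclusion.** The point holds in this limited form. From the text alone: wave labels do not fix the time since baseline, no rule assigns late joiners to a wave, and 8.8 counts follow-up on a different clock from 3.4.1. Conditionally: if individual slopes vary or correlation decays, the random-intercept model understates standard errors for slope and characteristic-by-time effects, with type I error of about 5–6%, 6–9% and 7–13% for three, four and five visits. Those rates rest on the assumed slope SD, residual SD and equal visit numbers, and apply to continuous outcomes. This should be corrected because primary objective 2 depends on these effects, but it does not undermine the study's descriptive results.

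**What to change.** - **8.4.1:** model actual time since first appointment as continuous, with a spline if needed. Code every record at its actual date, including a late joiner's entry assessment. Add a random slope for time, or a serial correlation structure suited to irregular times; an unstructured covariance needs common discrete waves and fits this design badly. Carry the change to 8.4.2.
- **3.4.1:** state which annual wave a late joiner enters next and the minimum gap from the entry assessment.
- **8.8:** define attendable waves on the first-appointment clock, limited to those after entry.

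The cost is mainly wording. The first-appointment date is on the eligibility form (4.3.2) and database entries are time-stamped (4.2.1); for forms transcribed later, the completion date should be used rather than the entry stamp. The statistical price is slightly wider confidence intervals for trajectory effects.
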